	4.1 Study Summary				
	4.2	Study	Population:	14	
5	STUDY ENROLLMENT AND WITHDRAWAL				
	5.1	Subjec	ct Inclusion Criteria	16	
	5.2	-			
6	STATISTICAL CONSIDERATIONS				
	6.1	Justification of effect size			
		6.1.1	· iis signissi		
		6.1.2	Minimum Clinically Important Difference		
		6.1.3	3		
		6.1.4			
7	LITER	RATURE	REFERENCES	20	

4/24/19

LIST OF ABBREVIATIONS

AE Adverse Event/Adverse Experience

BMI Body Mass Index CC Clomiphene Citrate

DHEA-S Dihydroepiandrosterone sulfate

DHHS Department of Health and Human Services

FDA Food and Drug Administration
IRB Institutional Review Board

IRL Iowa River Landing

PCOS Polycystic Ovary Syndrome

PPCOS II Pregnancy in Polycystic Ovary Syndrome Study II

P4 Progesterone

PI Principal Investigator

SAE Serious Adverse Event/Serious Adverse Experience

UIHC University of Iowa Hospitals and Clinics

US United States

PROTOCOL SUMMARY

Title: Combined Letrozole and Clomid in Polycystic Ovary

Syndrome: A randomized control trial of combination of letrozole and clomiphene citrate or letrozole alone for the

treatment of infertility in women with polycystic ovary syndrome

Précis: This will be a single center, randomized controlled open trial of

letrozole versus letrozole and clomiphene citrate (CC) for one cycle. Women will be randomized in a 1:1 ratio to receive letrozole 2.5 mg or combination of letrozole 2.5 mg and clomiphene 50 mg for 5 days on days 3-7 of menstrual cycle. We will stratify the randomization by age (< 35 versus >35) and BMI (<30, > 30) to try to ensure equal groups to study. The women and their partners will be instructed to have regular intercourse with the intent to conceive during the cycle. Patients will have an ultrasound on between cycle day 12 -14 and will evaluate number of follicles (>15 mm), follicle size, endometrial thickness and pattern. Patients will have midluteal phase progesterone level drawn. The primary analysis

ovulatory rate in the two treatment arms.

Objectives: Primary: Cumulative ovulation rate determined by a mid-luteal

(day 21) phase progesterone level. Progesterone level > 3

will use an intent-to-treat approach to evaluate differences in

ng/mL will indicate ovulation.

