4 STUDY DESIGN

Treatment Design: This will be a single center, open trial of oral letrozole vs. combination of oral letrozole and clomiphene citrate in the treatment of infertility in patients with polycystic ovary syndrome. Patients will be randomized to receive either a dose of 2.5 mg of letrozole or 2.5mg of letrozole and 50 mg of CC for 5 days on cycle days 3 through 7 of the menstrual cycle. Patients will be monitored during the cycle with a mid-cycle ultrasound (cycle days 12-14) and a mid-luteal progesterone level (cycle day 21).

The study will last for -1 cycles or approximately -5 weeks.

Randomization will be stratified by age (< 35 versus \geq 35) and BMI (< 30 and \geq 30) to ensure equal groups to study. Randomization will be via a computer based central randomization to ensure adequate allocation concealment.

Enrollment will take approximately 18 months if ~ 3.89subjects are enrolled per month. Active subject participation will be through completion of -1 cycle. We will follow up with patient regarding pregnancy, delivery outcomes, and if information is not available via chart abstraction.

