6.1.2 Minimum Clinically Important Difference

Since this is a pilot study our goal is to balance the risk of avoiding a type 2 error and having an attainable sample size. We have set a benchmark of 30% difference between groups as a clinically meaningful.

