6.1.3 Significance Testing

Primary statistical analyses will invoke the intent-to-treat approach. Primary efficacy analysis will be performed by comparing the treatment groups with respect to the primary outcome of ovulation using Pearson chi-square test. Additional analysis will be performed using logistic regression model to adjust for other factors such as the randomization stratification of age and BMI and prior exposure to study medications. A per protocol analysis will also be performed.

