6.1.4 Sample Size calculations

A sample size of 31 subjects in each arm of the randomization yields 80% statistical power to prospectively demonstrate a 0.30 absolute difference in ovulation rate between treatment arms (0.50 for Letrozole and 0.83 for combined letrozole and CC) using the Pearson's chi-square test having a two-sided significance level of 0.05. The sample size has been inflated to 35/arm to allow for a dropout rate of 10%. Dropout rate in the PPCOS II trial was 19.5% in the letrozole group however this was a longer study in

which they did 5 cycles and also a more involved study than the one we are proposing. Since there are fewer visits, fewer surveys and shorter enrollment period we anticipate a lower dropout rate in this trial.

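### Randomisation is stratified by age and BMI but the primary Pearson chi-square test is not; a test stratified by the same factors is a cheap, optional improvement if allocation is restricted within strata

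*Combined protocol and SAP*

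**What the plan says.** Section 4 states that "Randomization will be stratified by age" and by BMI, with cuts at 35 years and 30, which gives four strata. The Précis in the Protocol Summary says the same ("We will stratify the randomization by age"). On method, Section 4 adds: "Randomization will be via a computer based central randomization to ensure adequate allocation concealment". The documents do not say how allocation is balanced within a stratum.

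Section 6.1.3 sets the primary test: "Primary efficacy analysis will be performed by comparing the treatment groups with respect to the primary outcome of ovulation using Pearson chi-square test". The strata appear in the next sentence, in a supportive role: "Additional analysis will be performed using logistic regression model to adjust for other factors such as the randomization stratification of age and BMI", together with prior exposure to the study drugs.

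Section 6.1.4 sizes the trial on the same unstratified test, a "chi-square test having a two-sided significance level of 0.05". It uses ovulation rates of 0.50 and 0.83, 31 per arm for 80% power, and 35 per arm after allowing for 10% dropout. Section 6.1.2 expresses the target as an absolute difference: "We have set a benchmark of 30% difference between groups as a clinically meaningful".

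**The concern.** A trial that balances its arms on two factors normally carries those factors into the test that decides the result. If allocation is balanced within strata and the strata predict ovulation, the true variance of the difference between arms is smaller than the variance Pearson uses, because Pearson still counts the between-stratum spread as noise. The test is then conservative: part of the 5% goes unused and some power is lost. At stake is a small amount of efficiency and a better calibrated test. The validity of the primary result is not in question.

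**Working it through.** **The plan's own figure.** Pooled-variance formula, two-sided 0.05, 80% power, rates 0.50 and 0.83 (mean 0.665, difference 0.33):

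n = [1.960·√(2·0.665·0.335) + 0.842·√(0.50·0.50 + 0.83·0.17)]² / 0.33² = (1.308 + 0.526)² / 0.1089 ≈ 30.9, so 31 per arm.

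Inflation: 31/0.90 = 34.4, so 35 per arm. Both figures reproduce. Exact enumeration of the Pearson test at 0.50 vs 0.83 gives 80.8% power at 31 per arm and 85.8% at 35.

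**The two tests.**
- Pearson: (p̂₁ − p̂₀)² / [p̄(1 − p̄)(1/n₁ + 1/n₀)].
- CMH, no continuity correction: [Σ(y₁ₛ − n₁ₛkₛ/nₛ)]² / Σ[n₁ₛn₀ₛkₛ(nₛ − kₛ)/(nₛ²(nₛ − 1))], summed over the four strata s. Here y₁ₛ is ovulations in one arm, kₛ all ovulations and nₛ all women in the stratum.

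Both are referred to chi-square on 1 degree of freedom.

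**Inputs.** From the documents: 70 randomised 1:1, four strata, two-sided 0.05. Power was run at 0.50/0.83 (the rates in Section 6.1.4) and at 0.50/0.80 (the 0.30 difference named in the same section). Assumed, because the documents are silent: 65% with BMI ≥30, 20% aged ≥35, no age effect, BMI odds ratio for ovulation from 1 to 4.5, and either blocks of 4 within strata or no restriction (coin-flip allocation). Either all 70 are analysed or 8 are lost at random (70 − 8 = 62 = 2 × 31). There were 150,000 simulated trials per scenario; the standard error of each paired difference is 0.02 to 0.08 point.

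**Change in power, CMH minus Pearson, in percentage points.**

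| Allocation | BMI odds ratio | 70 analysed, 0.50/0.80 | 70 analysed, 0.50/0.83 | 62 analysed, 0.50/0.80 | 62 analysed, 0.50/0.83 |
|---|---|---|---|---|---|
| Blocks of 4 | 1 | −0.7 | −0.6 | −1.4 | −1.1 |
| Blocks of 4 | 2 | 0.0 | +0.1 | −0.6 | −0.5 |
| Blocks of 4 | 2.7 | +0.8 | +0.4 | +0.1 | +0.1 |
| Blocks of 4 | 4.5 | +2.1 | +1.3 | +1.7 | +1.4 |
| Unrestricted | 1 | −2.2 | −1.9 | −2.6 | −2.4 |
| Unrestricted | 2 | −1.3 | −1.0 | −1.7 | −1.6 |
| Unrestricted | 2.7 | −0.3 | −0.2 | −0.6 | −0.6 |
| Unrestricted | 4.5 | +1.7 | +1.2 | +1.2 | +0.9 |

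In absolute terms, with blocks of 4, 70 analysed and an odds ratio of 4.5, power goes from 77.5% to 79.6% (0.50/0.80) and from 86.5% to 87.8% (0.50/0.83). With 62 analysed, strata that do not matter and rates of 0.50/0.83, CMH power is 80.2% under blocking and 78.3% without it.

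**Type I error, Pearson vs CMH, blocks of 4.**
- 70 analysed: 4.4% vs 4.7% at odds ratio 1; 3.3% vs 5.0% at 4.5.
- 62 analysed: 5.6% vs 5.1% at odds ratio 1; 4.5% vs 5.1% at 4.5.

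The exact size of Pearson at a common rate of 0.50 is 5.6% at 31 per arm and 4.3% at 35. The 5.6% is therefore discreteness of a small 2×2 table. It appears where the strata have no effect at all.

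**Sensitivity.** With blocks of 4, 62 analysed and 0.50/0.83, varying the mix (BMI ≥30 share 50% or 80%, age ≥35 share 10% or 35%) gives −1.3 to −1.1 points at odds ratio 1, −0.8 to −0.3 at 2, and +0.5 to +1.9 at 4.5.

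**The case against.** The strongest reply is that nothing is wrong. Pearson is valid after stratified randomisation, it is clearly named, the sizing matches it, and the stated purpose of stratifying is comparable groups, which is achieved whichever test is used. A model adjusted for the strata is already planned. All of this stands, and it is why the point is optional.

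The reply continues that the power gain is unproven. No section gives an age or BMI effect on ovulation, and every gain of a full point in the table needs an assumed odds ratio of 4.5. That also stands; the gain is conditional. Part of the apparent loss for CMH at 62 analysed, however, reflects Pearson rejecting slightly too often there (5.6%).

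On the estimate, an unadjusted risk difference would serve the absolute benchmark as well as a stratum-weighted one. The gain in precision from weighting is small: with 62 analysed at 0.50/0.83 and blocks of 4, mean interval width is 0.431 against 0.433 at an odds ratio of 2, and 0.420 against 0.433 at 4.5. Coverage of the Mantel-Haenszel interval was 93.8% to 94.3%, slightly under nominal. The case for reporting a risk difference with an interval rests on the benchmark being absolute, not on precision.

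A reader might also infer that the protocol should publish its block scheme. That is not asked for. In an open, single-centre trial, known small blocks within strata could make assignments predictable, which works against the concealment that Section 4 seeks.

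**Conclusion.** The point holds as a low-cost improvement. Under blocks of 4 and the assumed mix, CMH keeps its size at 4.7% to 5.1% while Pearson runs from 3.3% to 5.6%. The change in power is −1.4 to +2.1 points, and its sign depends on how strongly the strata predict ovulation.

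Three stronger readings are tempting and not supported:
- Ignoring the strata does not inflate the type I error. Its effect is conservatism, and the 5.6% comes from discreteness.
- The trial is not mis-sized on this account. The 31 and 35 per arm reproduce for the test and rates used.
- The strata are not left out of the plan; they are in the additional logistic model.

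The conclusion rests on allocation being restricted within strata, which stratified randomisation ordinarily implies but the documents do not state. Without restriction, and with strata that are not prognostic, the change costs 1.9 to 2.6 points. It is then not recommended unless a strong stratum effect is expected.

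**What to change.** Provided allocation is restricted within strata:
- In Section 6.1.3, make a CMH test over the four randomisation strata (age <35/≥35 by BMI <30/≥30, as in Section 4) the primary test of ovulation.
- Report a risk difference with its 95% CI, because the benchmark in Section 6.1.2 is an absolute difference.
- Keep the unadjusted Pearson test as a sensitivity analysis; the logistic model can stay as it is.
- Name the same primary test in Section 6.1.4.

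The cost is a few sentences, settled before outcome data are seen. The sample size need not change: under blocks of 4, with 62 analysed and strata that turn out not to matter, CMH still has about 80% power at the planned 0.50 vs 0.83. The price in that case is 0.6 to 1.4 points of power relative to Pearson.

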6.1.4 Sample Size calculations

A sample size of 31 subjects in each arm of the randomization yields 80% statistical power to prospectively demonstrate a 0.30 absolute difference in ovulation rate between treatment arms (0.50 for Letrozole and 0.83 for combined letrozole and CC) using the Pearson's chi-square test having a two-sided significance level of 0.05. The sample size has been inflated to 35/arm to allow for a dropout rate of 10%. Dropout rate in the PPCOS II trial was 19.5% in the letrozole group however this was a longer study in

which they did 5 cycles and also a more involved study than the one we are proposing. Since there are fewer visits, fewer surveys and shorter enrollment period we anticipate a lower dropout rate in this trial.

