6 STATISTICAL CONSIDERATIONS

6.1 Justification of effect size

6.1.1 Prior Studies

The primary outcome is ovulation, defined by a mid-luteal progesterone level > 3 ng/mL. There is data demonstrating the cumulative live birth rate with clomiphene and letrozole from the PPCOS II trial. This trial compared letrozole to clomiphene demonstrated that letrozole was associated with a higher cumulative ovulation rate (61.7% vs. 48.3%, P<0.001) among women with polycystic ovary syndrome and the rate of ovulation after one treatment cycle with letrozole 2.5 mg was 50%.9 Unfortunately, there is no comparative quality data from randomized trials of the combination of letrozole and CC. There is one study that prospectively reviewed treatment outcomes using a combination of letrozole and clomiphene who had previously failed CC for 6 cycles and letrozole for 4 cycles. This study enrolled 100 patients and showed an ovulatory rate (defined by development of dominant follicle) of 82.9% of cycles (213/257) with the combination treatment. 10 However, this study was not randomized and used a limited population of women with PCOS that were resistant to both clomiphene and letrozole alone. Additionally, patients received Gonal-f on day 11 if a dominant follicle was present and then received hCG trigger when the follicle was >18 mm in size followed by IUI 36-38 hours later.

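### Section 6.1.4 claims 80% power for a 0.30 difference, but its 31 per arm matches 0.50 versus 0.83 (0.33); power at the 30-point benchmark is about 71%

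*Combined protocol and SAP*

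**What the plan says.** Section 6.1.2 fixes the target: "We have set a benchmark of 30% difference between groups as a clinically meaningful". It gives no pair of rates.

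Section 6.1.4 then makes the power claim. It opens "A sample size of 31 subjects in each arm of the randomization yields 80% statistical power" and says this is enough to "demonstrate a 0.30 absolute difference in ovulation rate between treatment arms (0.50 for Letrozole and 0.83 for combined letrozole and CC"). The test is specified as "using the Pearson's chi-square test having a two-sided significance level of 0.05". A 10% dropout allowance raises 31 to 35 per arm, 70 in total.

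Section 6.1.1 gives the background for both rates. The letrozole rate of 50% is ovulation after one cycle in the earlier randomized trial of letrozole against clomiphene. For the combination, the one available study "showed an ovulatory rate (defined by development of dominant follicle) of 82.9% of cycles (213/257"). The same section cautions that this study was not randomized, was limited to women resistant to both drugs, and added Gonal-f and an hCG trigger.

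**The concern.** The sentence in 6.1.4 contradicts itself: 0.83 − 0.50 = 0.33. Nothing elsewhere in the document reconciles 0.33 with 0.30. One of the two figures drove the sample size, and the reader needs to know which.

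This is more than rounding, because 0.30 is the difference the plan itself calls clinically meaningful. If N was computed for 0.33, the plan credits the trial with 80% power at its benchmark and the trial does not have it. Section 2.2 treats showing a better ovulation rate as the step before a larger live-birth trial. A non-significant result could therefore be read as stronger evidence against a 30-point benefit than the design supports.

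The 0.83 also coincides with the 82.9% from the uncontrolled study. The document does not say that this is its source, but the match is close. If so, the calculation rests on an external rate that the plan itself qualifies, measured by dominant follicle rather than by progesterone above 3 ng/mL, and not on the benchmark in 6.1.2.

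**Working it through.** **Inputs.** Letrozole rate 0.50, combination rate 0.83, stated difference 0.30, Pearson chi-square, two-sided alpha 0.05, 80% power, 31 per arm, 10% dropout (all 6.1.4); benchmark of 30% (6.1.2); 1:1 allocation (Protocol Summary). The benchmark is read as 30 percentage points because 6.1.4 calls the difference absolute. With letrozole at 0.50 that means 0.50 versus 0.80; the 0.80 is inferred and is not printed in the plan.

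**Formulas** (normal approximation to the uncorrected chi-square, p̄ the mean of the two rates):

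n per arm = [1.960·√(2p̄(1−p̄)) + 0.842·√(p₁(1−p₁)+p₂(1−p₂))]² / (p₂−p₁)²

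power = Φ{ [(p₂−p₁)·√n − 1.960·√(2p̄(1−p̄))] / √(p₁(1−p₁)+p₂(1−p₂)) }

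**Step 1: reproduce the plan's figure, 0.50 versus 0.83.** p̄ = 0.665; 2p̄(1−p̄) = 0.4456; p₁(1−p₁)+p₂(1−p₂) = 0.3911.

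n = (1.308 + 0.526)² / 0.33² = 3.366 / 0.1089 = 30.9, so 31 per arm. Power at 31 is Φ(0.846) = 80.1%. The dropout step gives 31 / 0.90 = 34.4, so 35. The plan's 31 and 35 both reproduce.

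**Step 2: the benchmark, 0.50 versus 0.80.** p̄ = 0.65; 2p̄(1−p̄) = 0.4550; p₁(1−p₁)+p₂(1−p₂) = 0.4100.

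n = (1.322 + 0.539)² / 0.30² = 3.463 / 0.0900 = 38.5, so 39 per arm. With 10% dropout, 39 / 0.90 = 43.3, so 44 per arm (88 in total).

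**Step 3: power with the planned numbers.** "Exact" sums the binomial probabilities of all outcomes that the uncorrected chi-square rejects.

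| True rates | Evaluable per arm | Power, normal approximation | Power, exact |
|---|---|---|---|
| 0.50 vs 0.83 | 31 | 80.1% | 80.8% |
| 0.50 vs 0.83 | 35 | 84.8% | 85.8% |
| 0.50 vs 0.80 | 31 | 70.7% | 71.4% |
| 0.50 vs 0.80 | 35 | 76.0% | 77.1% |

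At the benchmark the type II error with 31 per arm is 1 − 0.707 = 29%, against the 20% implied.

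**Step 4: detectable difference.** With letrozole at 0.50, the difference detectable with 80% power is 0.33 at 31 per arm and 0.31 at 35.

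**Step 5: does another reading rescue the claim?**
- Other two-sided approximations for 0.50 versus 0.80 at 31 per arm give 71.7% (arcsine) and 74.2% (unpooled variance). A continuity correction raises the requirement to 45 per arm.
- Keeping 0.83 and moving letrozole to 0.53 gives 37 per arm and 72.7% power at 31.
- A one-sided 0.05 test of 0.50 versus 0.80 does give n = 30.2, so 31, but 6.1.4 specifies two-sided.
- A 30-point difference at a higher letrozole rate, such as 0.61 versus 0.91, also gives 31 (n = 30.6), but 6.1.4 states 0.50.
- Reading 30% as relative gives 0.50 × 1.30 = 0.65, further still from 0.83.

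**The case against.** The best defence is that everything needed is printed in one sentence. The rates, test, alpha, power and N agree with one another, and a careful reader can see that 0.50 versus 0.83 was powered. On that view the fault is one wrong label, in a study that calls itself a pilot and says openly that it trades type II error against an attainable size. That is fair as far as the calculation goes: 31 and 35 are right for 0.50 versus 0.83, and the slip does not bias the primary test or affect its type I error. It does not rescue the power claim, because the label is also the benchmark in 6.1.2, and a trade-off against type II error should be made with the correct type II error.

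A second argument is that 71% is the low end. The trial enrols 35 per arm and analyses by intention to treat, so with every woman evaluable the power is 76–77% and the detectable difference, 0.31, is close to the target. This stands as a reason to quote both figures. But the plan attaches its own 80% to 31 per arm, so 71% is the like-for-like comparison, and even with no dropout the power stays below 80%.

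Third, the benchmark pair is inferred, and power at a 30-point difference depends on the letrozole rate. That is correct, and the figures here are conditional on 0.50, the rate the plan uses.

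Finally, the plan contains no rule for interpreting a null result, so over-interpretation is a risk rather than a certainty. The limits of the 82.9% study are already disclosed, and its suitability as a planning rate is a separate matter from the arithmetic.

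**Conclusion.** The concern holds. Section 6.1.4 attaches 80% power to a 0.30 difference, whereas its sample size delivers that power for 0.33. At the plan's own benchmark, power is about 71% with 31 evaluable per arm and 76–77% with 35, and 80% would need 39 evaluable per arm, eight more than planned (8/31, about 26%). These figures assume a letrozole ovulation rate of 0.50, a benchmark of 30 percentage points, 1:1 allocation and the uncorrected two-sided chi-square test at 0.05. The power statement for the primary endpoint is wrong as written and must be corrected.

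**What to change.** Reword 6.1.4 to say that 31 evaluable women per arm give 80% power for an absolute difference of 0.33 (0.50 versus 0.83), and about 71% power for the 0.30 benchmark of 6.1.2 (0.50 versus 0.80), rising to 76% if all 35 per arm are evaluable. State the source of the 0.83 in the same place, and make clear that the calculation uses that rate and not the benchmark.

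N stays at 70. The cost is a text correction and a less favourable power figure at the benchmark; no procedure, analysis or patient number changes. If the sponsor instead wants 80% power at 0.30, the size would be 39 evaluable per arm, or 44 per arm (88 in total) with the plan's 10% dropout, which is 18 more women. That is optional and is not needed to make the statement true.
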